6.5 Prior and Concomitant Therapy

Concomitant treatment is any drug or substances administered between screening and end of study (Week 24).

Allowed Concomitant Therapy:

- Medications for chronic medical conditions are allowed at a stable dose during the study provided the subject has been on a stable dose for at least 3 months prior to randomization.
- Cholinesterase inhibitors and memantine are allowed provided the therapy has been stable for at least 3 months prior to screening and that the patient stays on a stable dose during the study.

- Anticholinergic medications allowed include the following: Ranitidine, Loratadine, fexofenadine, cetirizine, cyclobenzaprine

Disallowed Concomitant Therapy:

- Meperidine (Demerol), Propoxyphene and Tramadol
- Ciprofloxacin and other CYP1A2 Inhibitors
- MAO inhibitors such as but not limited to the following: Isocarboxazid, Phenelzine, Selegiline, and Tranylcypromine
- Dextromethorphan and Nuedexta
- St. John's wort
- Levodopa/Carbidopa
- Theophylline
- Sympathomimetic medications
- Hydroxyzine
- Diphenhydramine
- Scopolamine
- Cyproheptadine
- Oxybutynin
- Fesoterodine
- Solifenacin
- Darifenacin
- Dicyclomine
- Glycopyrrolate
- Antipsychotics such as but not limited to the following most commonly used antipsychotic medications: Haloperidol, Quetiapine, Ziprasidone, and Risperidone

Antidepressants are excluded with the following exceptions:

- Amitriptyline ≤ 25 mg/d
- Nortriptyline ≤ 50 mg/d
- Trazodone ≤ 50 mg/d
- Citalopram ≤ 20 mg/d
- Escitalopram ≤ 10 mg/d
- Sertraline ≤ 100 mg/d
- Paroxetine ≤ 20 mg/d
- Mirtazapine ≤ 30 mg/d
- Buspirone ≤ 30 mg/d
- Fluoxetine ≤ 40 mg/d
- Bupropion ≤ 150 mg/d
- Duloxetine ≤ 60 mg/d
- Venlafaxine ≤ 125 mg/d
- No hypnotics the night prior to or day of PET scan preceding the scan

High tyramine-containing foods will be avoided:

- Sausages, salami, pickled herring
- Fava beans
- Tap beers, non-pasteurized beers
- Sauerkraut, yeast extract, soybean products including soy sauce

- Aged cheeses

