KEY INCLUSION CRITERIA	
 • Males or females 50 to 90 of age inclusive • Diagnosis of probable AD (NINCDS-ADRDA criteria) • Positive fluorodeoxyglucose PET ([¹⁸F]-FDG PET) scan compatible with AD as determined by the ADM Diagnostics LLC (ADMdx) criteria at screening • Must be willing to undergo ¹⁸F-AV-1451 Tau PET scan at Baseline and Week 24 visits • MMSE = 12-26 (inclusive) • Must have a study partner who is able and willing to comply with all required study procedures

	
 • Have at least eight years of education and should have previously (in pre-AD condition) been capable of reading, writing, and communicating effectively with others in English • If receiving therapy with a cholinesterase inhibitor and/or memantine, the dose of these agents has been stable for at least 60 days prior to screening
KEY EXCLUSION CRITERIA	
 • Any non-AD neurological disease • MRI findings indication of a non-AD diagnosis • Screening laboratory studies that are 1.5 times above or below the highest and lowest range of normal for each test, respectively • History of melanoma; history of malignancy within the past five years with the exception of basal cell or squamous cell carcinoma, in-situ cervical carcinoma, or localized prostate cancer
DISALLOWED MEDICATIONS	
 • Meperidine (Demerol) • Ciprofloxacin • MAO inhibitors such as but not limited to the following: Isocarboxazid, Phenelzine, Selegiline, and Tranylcypromine. • Dextromethorphan and Nuedexta • Hydroxyzine • Diphenhydramine • Scopolamine • Cyproheptadine • Oxybutynin • Fesoterodine • Solifenacin • Darifenacin • Dicyclomine • Glycopyrrolate • Antipsychotics such as but not limited to the following most commonly used antipsychotic medications: Haloperidol, Quetiapine, Ziprasidone, and Risperidone
MEDICATIONS WITH LIMITED DOSES	
Antidepressants are excluded with the following exceptions:
 
 • Amitriptyline \leq 50 md/d • Trazodone \leq 100 mg/d • Citalopram \leq 20 mg/d • Escitalopram \leq 10mg/d • Sertraline \leq 100 mg/d • Paroxetine \leq 30 mg/d • Mirtazapine \leq 30 mg/d • Buspirone \leq 30mg/d • Fluoxetine \leq 40 mg/d • Bupropion \leq 150 mg/d • Duloxetine \leq 60 mg/d • Venlafaxine \leq 125 mg/d • No hypnotic the night prior to or day of PET scan preceding the scan

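### The Synopsis and Protocol 6.5 give different daily caps for three permitted antidepressants and disagree on whether a fourth is permitted at all

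*Protocol*

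**What the plan says.** The Synopsis, in its row on medications with limited doses, opens with "Antidepressants are excluded" and then names exceptions, each with a daily maximum. Protocol 6.5 opens its own list with "Antidepressants are excluded with the following exceptions". Both use the same logic: a drug not named is not allowed, and a named drug is allowed up to its cap.

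The entries that conflict are:

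- Amitriptyline: "Amitriptyline \leq 50 md/d" in the Synopsis, "Amitriptyline ≤ 25 mg/d" in 6.5. The backslash code is how the text extraction shows the less-than-or-equal sign. The Synopsis unit is a misprint and is read here as mg/d.
- Trazodone: "Trazodone \leq 100 mg/d" in the Synopsis, "Trazodone ≤ 50 mg/d" in 6.5.
- Paroxetine: "Paroxetine \leq 30 mg/d" in the Synopsis, 20 mg/d in 6.5.
- Nortriptyline: "Nortriptyline ≤ 50 mg/d" in 6.5, with no entry in the Synopsis.

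Both lists are current text of Amendment 5. The summary of changes records that allowed antidepressants were clarified (Amendment 3) and that allowed medications were added (Amendments 3 and 4). It gives no doses, so it does not show which list reflects the latest decision.

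**The concern.** Site staff deciding whether a patient's existing antidepressant is acceptable get a different answer depending on which part of the Protocol they open. Section 6.5 counts concomitant treatment from screening onward, so the question arises at entry as well as during treatment. With three sites, the same prescription could be accepted at one and refused at another, and each site could point to current text in support.

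There is also a smaller consequence for the analysis. The SAP's per-protocol population (SAP section 4) leaves out patients with protocol violations that affect the analysis. If a patient's dose lies between the two caps, whether a violation occurred at all depends on the list consulted. Settling that after the data are seen would add a discretionary judgement to the per-protocol set.

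**Working it through.** There is no sample-size, power or error-rate figure to reproduce. The check is a line-by-line comparison of the two lists (daily maximum in mg).

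| Drug | Synopsis | Section 6.5 | Ratio, Synopsis to 6.5 |
|---|---|---|---|
| Amitriptyline | 50 | 25 | 50/25 = 2.0 |
| Trazodone | 100 | 50 | 100/50 = 2.0 |
| Paroxetine | 30 | 20 | 30/20 = 1.5 |
| Nortriptyline | not listed | 50 | none |
| Citalopram | 20 | 20 | 1 |
| Escitalopram | 10 | 10 | 1 |
| Sertraline | 100 | 100 | 1 |
| Mirtazapine | 30 | 30 | 1 |
| Buspirone | 30 | 30 | 1 |
| Fluoxetine | 40 | 40 | 1 |
| Bupropion | 150 | 150 | 1 |
| Duloxetine | 60 | 60 | 1 |
| Venlafaxine | 125 | 125 | 1 |

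Count: the Synopsis names 12 drugs and 6.5 names 13. Of the 12 shared drugs, 9 agree and 3 differ. One drug is in 6.5 only.

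The range in which the two sections give opposite answers follows directly:

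- amitriptyline above 25 and up to 50 mg/d: permitted by the Synopsis, excluded by 6.5;
- trazodone above 50 and up to 100 mg/d: the same (75 mg/d would be an example);
- paroxetine above 20 and up to 30 mg/d: the same;
- nortriptyline up to 50 mg/d: permitted by 6.5, excluded by the Synopsis.

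The disagreement runs in both directions. The Synopsis is looser on three drugs and 6.5 is looser on one, so neither section is simply a stricter form of the other.

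Next, whether other text settles it. The numbered exclusion criteria in 5.2 contain no antidepressant dose cap, and criterion 16, on disallowed medications, does not name these drugs. No statement was found that the body overrides the Synopsis or the reverse.

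Last, which analysis sets could be touched:

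- Primary FDG analysis (Protocol 11.2, SAP section 5): patients with a screening and an end-of-study scan of acceptable quality. Medication plays no part.
- SAP ITT population (section 4): all consented randomized patients, whatever their violations. Not affected.
- Protocol per-protocol population (Synopsis and 11.2): completion plus pill count of 80% to 120%. Medication plays no part.
- SAP per-protocol population (section 4): also requires that the entry criteria were met and that no violation affects the analysis. This is the only definition the conflict can reach, and SAP section 9 uses it to repeat the clinical analyses.

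**The case against.** The strongest reply is that this is a drafting slip with little statistical weight. Protocol 9.2 discourages changes to medication after randomization but continues follow-up regardless of compliance with the restrictions. For drugs excluded because they confound cognitive outcomes, it also requires neither stopping study drug nor removal from the ITT analysis. The primary FDG set depends on scans alone. All of that stands, and it limits the finding.

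A second reply is that the body of a protocol customarily governs over its synopsis. The documents do not say so, and site staff commonly work from a synopsis. This reply does not remove the conflict.

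Three stronger readings are tempting but not supported:

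- A reader might infer that these caps are safety limits for use with an MAO inhibitor. The Protocol never says why they exist. Sections 1.3 and 10.1 call drug interactions a historical concern with this class, but discuss tyramine-rich food and sympathomimetics and do not mention antidepressants. The reason 9.2 gives for excluding certain medications is confounding of cognitive outcomes. A safety purpose is a reasonable inference, but it remains an inference.
- A reader might infer that the formal eligibility criteria contradict each other. They do not, because 5.2 is silent on these caps. The conflict lies between two concomitant-medication lists whose wording excludes what they do not permit.
- A reader might infer that the conflict determines per-protocol membership. It may affect it. Under the SAP a breach counts only if it is judged to affect the analysis, and under the Protocol's own definition it does not count at all.

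**Conclusion.** This is an internal inconsistency and is wrong as written. Two current lists that serve the same purpose differ on 3 of 12 shared caps, by factors of 2, 2 and 1.5, and on whether one further drug is allowed. Sites following the Protocol can reach opposite decisions on the same prescription, and nothing in the documents resolves which list applies.

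The practical size is unknown: the documents do not say how many patients take these drugs at doses in the disputed ranges. The possible statistical effect is confined to the SAP's per-protocol repeat of the clinical analyses. The definitions of the primary FDG set and the ITT set are untouched.

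The conclusion assumes that the Synopsis unit for amitriptyline is mg/d, and that the differences are in the Protocol itself and were not introduced by text extraction. The second assumption is safe, since three separate legible lines differ and one whole entry is absent. Even with amitriptyline set aside, two caps and one drug would still conflict.

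**What to change.** The Synopsis and section 6.5 must be reconciled into a single list with one limit per drug, and the amitriptyline unit corrected. The medical lead should make that decision; no limit is proposed here, and no view is taken on which existing figure is right. It would help to state the purpose of the caps, to say whether they apply at entry, during treatment or both (with a cross-reference in 5.2 if at entry), and to keep the list in one place that the other section cites.

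Enrolled patients' concomitant-medication records should then be checked against the reconciled list. Before unblinding, the SAP should say whether exceeding a cap counts as a violation that affects the analysis for the per-protocol population.

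The cost is a short protocol amendment, notice to the three sites, and a records review for at most the 50 planned patients. No new data collection is needed, and neither the sample size nor the primary analysis changes.

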6.6 Blinding of Study Drug

An unblinded pharmacist or unblinded study personnel will administer and dispense the trial medication to the subjects to maintain the double-blinding of the study.

6.7 Receiving, Storage, Dispensing and Return

6.7.1 Receipt of Drug Supplies

All drugs for the study will be shipped to each of the three sites of the Cleveland Clinic Lou Ruvo Center for Brain Health. Upon receipt of the study treatment supplies, an inventory will be performed and a drug receipt log filled out and signed by the person accepting the shipment. The unblinded pharmacist or unblinded study staff will count and verify that the shipment contains all the items noted in the shipment inventory. Any damaged or unusable study treatment product in a given shipment will be documented in the study files. Active drug and the matching placebo soft capsules will be provided by Teva Pharmaceuticals.

6.7.2 Storage

Rasagiline can be stored at room temperature. High temperatures will be avoided. The drug will be protected from light. No special temperature controls are necessary beyond those of room temperature.

6.7.3 Packaging of Study Drug

Study active medication and placebo will be packaged in 1-month supply bottles. There will be a total of 40 capsules in a bottle of either the rasagiline drug or the placebo. Each participant will return study medication bottles (including any unused study medication) at each visit for drug accountability purposes.

6.7.4 Dispensing of Study Drug

Participants will receive study drug or placebo in one-month supply bottles. At Baseline (Visit 2), the randomized subject will be given one (1) bottle containing either the active drug or the placebo. All subjects will be instructed to take one 0.5 mg tablet once a day for the first 4 weeks. A dosing instructions sheet will also be provided to all subjects as a dosing guide. At Visit 3 (Week 4), subjects will be seen at the clinic and, if there is no reason to discontinue therapy, will be advanced and instructed to take one 1 mg tablet once daily for 4 weeks. Patients will then be seen at Visit 4 (Week 8) at which time they will receive a 4-month supply of the study medication. Regular study drug reconciliation will be performed to document drug dispensed; drug consumed, and drug remaining. This reconciliation will be logged on the drug reconciliation form, signed and dated by the study coordinator.

6.7.5 Return or Destruction of Study Drug

There will be a final reconciliation of the study drug at the conclusion of the study. The reconciliation will be logged onto the drug reconciliation form, signed and dated. Any discrepancies noted will be investigated, resolved and documented prior to return of unused study drug.

7. DESCRIPTION OF STUDY VISITS

7.1 Visit 1 – Screening (Days -60 to -1)

Subjects will undergo all screening procedures within 60 days prior to baseline visit to confirm the study eligibility.

The following activities will be completed:

- Obtain IRB approved written informed consent from the subject and the subject's legal representative in accordance with regulation before initiating any procedures for both the main protocol and the **¹⁸F-AV-1451 imaging companion** protocol
- Assess inclusion and exclusion criteria
- Obtain demographic data
- Obtain medical history and review medications
- Obtain history of prior procedures (radiation/PET)
- Record prior medication within the last 3 months
- Obtain Ohio State University Traumatic Brain Injury Identification Method (OSU TBI-ID) Questionnaire for the **¹⁸F-AV-1451 TAU imaging companion protocol**.
- Perform Mini Mental State Examination (MMSE)
- Perform physical and neurological examinations
- Record orthostatic vital signs, body weight and height
- Obtain standard single 12 lead EKG
- Collect non-fasting blood sample for routine laboratory test including:
 - Hematology
 - Blood chemistry
 - Liver function
 - TSH
 - B12
- Collect urine sample for screening urinalysis (UA)
- Obtain MRI: T1 sequence and two-dimensional T2*-GRE to detect micro-hemorrhages and T2 FLAIR sequences to identify ARIA-E
- Obtain fluorodeoxyglucose (FDG) PET imaging
- Obtain **¹⁸F-AV-1451** Tau imaging pending positive FDG PET imaging results

The screening visit MRI, FDG PET imaging and **¹⁸F-AV-1451** Tau PET imaging visits will be done on separate visits.

POST ¹⁸F-AV-1451 TAU IMAGING FOLLOW-UP PHONE CALL

A follow-up phone call to the participant or the caregiver will be conducted between 2 and 3 business days after the imaging visit, but not before 48 hours post-injection, to confirm participant well-being and to collect information about any new adverse events. If both of these days are not business days, the follow-up phone call can occur the following business day.

7.2 Visit 2 – Baseline (Day 1)

Patients will be randomized within 60 days from the first day of screening.

The following activities will be completed PRIOR to dosing:

- Review Inclusion/Exclusion qualification
- Review laboratory studies performed at Screening Visit (laboratory results should be normal to continue randomization of subject)
- Review of MRI and PET Scan results
- Inquire about occurrence of adverse events since previous visit and changes to concomitant medications

If subject continues to be eligible for the study, he/she may be entered into the double-blind randomization phase and procedures listed below will occur:

- Record vital signs and body weight
- Perform Mini Mental State Examination (MMSE)
- Collect blood sample for ApoE genotyping test
- Collect blood sample for biomarker measures including:
 - Serum A β 40 and 42
 - sAPP- α , sAPP- β , Isoprostanes
 - Cytokines and other measures relevant to AD
- Perform the following assessments:
 - ADAS-Cog 11
 - CGIC
 - NPI
 - ADCS-ADL
 - Digit Span
 - COWAT
 - QoL-AD/Study Partner
- Dispense double blind study medication to patient and caregiver for outpatient dosing, with instructions to return bottle and unused study medication to clinic at next visit.
- Provide instructions to caregiver/subject on outpatient dosing, including storage, administration, and compliance assessment.

Patients will be given a one-month supply of medication at this visit. The dosing instruction at this visit is to take one 0.5mg capsule of study drug or matching placebo once a day for one month. Leftover medications will be brought to clinic visits for accountability.

7.3 Visit 3 – Week 4

This visit will occur at the end of Week 4 with a visit window of +/- 5 days.

The following activities will be completed:

- Record orthostatic vital signs and body weight
- Inquire about occurrence of adverse events since previous visit and any changes to concomitant medications since Baseline Visit
- Perform the following assessments:
 - ADAS-Cog 11
 - CGIC
 - NPI
 - ADCS-ADL
 - Digit Span
 - COWAT

- Assess drug adherence and accountability of study medication
- Dispense double blind study medication to patient and caregiver for outpatient dosing, with instructions to return bottle to clinic at next visit.
- Provide instructions to caregiver/subject on outpatient dosing, including storage, administration, and compliance assessment.

This is a check-up visit to determine if patients are able to tolerate the medication. If so, they will be instructed to take the medication to an increased dosage of 1 mg rasagiline or matching placebo tablet once daily.

7.4 Visit 4 – Week 8

This visit will occur at the end of Week 8 with a visit window of +/- 5 days.

The following activities will be completed:

- Record orthostatic vital signs and body weight
- Inquire about occurrence of adverse events since previous visit and any changes to concomitant medications since Baseline Visit
- Perform the following assessments:
 - ADAS-Cog 11
 - NPI
 - ADCS-ADL
 - Digit Span
 - COWAT
- Assess drug adherence and accountability for study medication
- Dispense double blind study medication to patient and caregiver for outpatient dosing, with instructions to return bottle to clinic at next visit.
- Provide instructions to caregiver/subject on outpatient dosing, including storage, administration, and compliance assessment.

This is a check-up visit to determine if patients are able to tolerate the medication. If so, they will be instructed to take the medication with the continued dosage of 1 mg rasagiline or matching placebo tablet once daily.

7.5 Visit 5 – Week 24

This visit will occur at the end of Week 24 with a visit window of +/- 5 days. This visit concludes the treatment phase of the study.

The following activities will be completed:

- Record orthostatic vital signs and body weight
- Obtain standard single 12 lead EKG
- Review medical history
- Inquire about occurrence of adverse events since previous visit and changes to concomitant medications
- Collect non-fasting blood sample for routine lab tests including:
 - Hematology
 - Blood chemistry
 - Liver function
 - TSH

- Collect blood sample for biomarker measures including:
 - Serum A β 40 and 42
 - sAPP- α , sAPP- β , Isoprostanes
 - Cytokines and other measure relevant to AD
- Perform the following assessments:
 - MMSE
 - ADAS-Cog 11
 - CGIC
 - NPI
 - ADCS-ADL
 - Digit Span
 - COWAT
 - QoL–AD/Study Partner
- Perform physical and neurological examinations
- Assess drug adherence and accountability of study medication
- Obtain fluorodeoxyglucose (FDG) PET imaging
- Obtain Ohio State University Traumatic Brain Injury Identification Method (OSU TBI-ID) Questionnaire for the 18F-AV-1451 TAU imaging companion protocol.
- Obtain ¹⁸F-AV-1451 Tau PET imaging. This could be done **14 days before or 7 days after last study treatment dose.**

This visit will be the end of the treatment phase and participants will then be followed up for safety 4 weeks post-treatment.

POST ¹⁸F-AV-1451 TAU IMAGING FOLLOW-UP PHONE CALL

A follow-up phone call to the participant or the caregiver will be conducted between 2 and 3 business days after the imaging visit, but not before 48 hours post-injection, to confirm participant well-being and to collect information about any new adverse events. If both of these days are not business

7.6 Visit 6 – Follow-up Visit/End of Study/Early Discontinuation (Week 28)

This visit will occur at the end of Week 28 with a visit window of +/- 5 days. This will be a follow-up visit after the treatment phase.

The following activities will be completed:

- Record orthostatic vital signs and body weight
- Perform the following assessments:
 - ADAS-Cog 11
 - CGIC
 - NPI
 - ADCS-ADL
 - Digit Span
 - COWAT

7.7 Unscheduled Visits

Patients will have unscheduled visits if they report unusual side effects. If the patient reports abrupt worsening of cognition, or experiencing one of the reported adverse effects, the patient will be evaluated by the study clinician.

7.8 Study Calendar of Procedures

The Schedule of Activities (Table 2) provides an overview of the protocol visits and procedures. Refer to Study Procedures (Section 8.0) for detailed information on each procedure and assessment required for compliance with the protocol.

Table 2 Schedule of Activities

	Screening	Treatment Phase				Follow-Up
Visit #	Visit 1	Visit 2/ Baseline	Visit 3	Visit 4	Visit 5/ EOT	Visit 6/ EOS/ Early Discontinuation
Visit Week	Week -8	Week 0	Week 4	Week 8	Week 24	Week 28
Visit Window	Days -60 to -1	Day 1	(± 5 days)	(± 5 days)	(± 5 days)	(± 5 days)
Informed consent	X					
Demographic data	X					
Medical history	X				X	
Review of medications	X				X	
Inclusion/Exclusion criteria	X					
Height	X					
Body weight	X	X	X	X	X	X
Hematology, Chemistry, TSH, B12 liver function, and UA	X				X	
ApoE genotyping		X				
AD biomarkers		X			X	
ECG	X				X	
Orthostatic vital signs	X	X	X	X	X	X
Physical & Neurological Examinations	X				X	
OSU-TBI-ID	X				X	
MMSE	X	X			X	
ADAS-Cog 11		X	X	X	X	X
CGIC		X	X		X	X
ADCS-ADL		X	X	X	X	X
NPI		X	X	X	X	X
Digit Span		X	X	X	X	X
COWAT		X	X	X	X	X
QoL-AD/Study Partner		X			X	
MRI	X					
FDG PET	X				X	
¹⁸ F-AV-1451 Tau PET	X				X ^[2]	
FU ¹⁸ F-AV-1451 PET Phone Call ^[1]	X				X	
Record adverse events		X	X	X	X	X
Dispense trial medication		X	X			
Drug adherence/ accountability assessment			X	X	X	X

- ^[1] The Follow-up ¹⁸F-AV-1451 Tau Pet Phone Call will be conducted between 2 and 3 business days after the imaging visit, but not before 48 post inject to confirm participant well-being.
- ^[2] Week 24 visit ¹⁸F-AV-1451 Tau PET can be done **14 days before or 7 days after the last study treatment dose.**

8. Study Specific Procedures

